- Number of randomised patients included in the final analyses at the primary endpoint(s)

Withdrawal and follow-up

Participants may be discontinued from the trial at any time. They can either withdraw from the intervention alone but remain on follow-up or they can withdraw completely from the trial. Unless a participant explicitly withdraws their consent, they will be followed-up wherever possible and data collected as per the protocol until the end of the trial. The number of withdrawals from the trial will be summarised by treatment arms, that is, how many participants withdrew from intervention alone but remained on follow-up and how many withdrew completely from the trial. In addition, the withdrawal timings will also be summarised by treatment arms. It will include withdrawals after randomisation but before hospital discharge, and withdrawals after hospital discharge but before 28 days follow-up. The withdrawal decision i.e. decision made by the participant, consultant, clinical team, antibiotic stopped due to futility, required >21 days of antibiotics post randomisation and

other, will be summarised by treatment arms. Follow-up rates will be computed at the 28-day and 90-day follow-up time-points. At 90 days, only all-cause mortality data will be collected using NHS digital and the Intensive Care National Audit and Research Centre.

Baseline patient characteristics

The baseline demographic characteristics and pre-randomisation clinical measures of all randomised participants will be summarised by treatment arms. Moreover, important process data (e.g. date and time of hospital admission and ICU/HDU admission) will also be collected and summarised by treatment arms. Continuous data will be summarised using the statistics the number of participants (n), mean, standard deviation (sd), median and interquartile range (IQR) whereas categorical data will be summarised using the statistic the number (%) of participants. The table below lists the demographic, clinical measures and process variable data that will be collected and summarised.

- Age
- Gender
- Suspected septic shock
- Surgery within last 72 hours
- Core body temperature
- White cell count
- Critical care admission category
- Critical care origin
- Initial care bundle
- qSOFA score
- SOFA score
- APACHE II score
- Infection data:
 - Community/hospital acquired infection
 - Site of infection
 - Causative microorganism identified for infection
 - If yes to the above, detail pathogen

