The primary effectiveness analyses will assess whether any of the biomarker interventions are better than standard care. The primary analysis approach for the duration of antibiotics will be intention-to-treat (ITT). ITT analysis will consist of all randomised patients and will assess the effect of treatment assignment. For the ITT analysis, linear mixed effects regression models will be fitted to estimate the treatment effect having adjusted for age, gender and the stratification variables (sepsis severity, recruiting centre (random effect) and surgery within the last 72 hours). After fitting the model, we will investigate the validity of the assumption of normality. Alternative methods of analyses will be considered if the distribution of the primary effectiveness outcome is non-normal. In this trial, participants may die before antibiotic therapy is discontinued. In such cases the outcome is undefined and is referred to as 'truncated by death'. A crude comparison between the survivors on each treatment arm may give rise to biased outcome comparisons. Therefore, we will consider undertaking some sensitivity analyses to estimate treatment effect having account for the deaths. This will explore different approaches to analysis of ICU trials, that allow incorporation of multiple relevant outcomes, including death, into a single overall measure (e.g., the win ratio⁸, global ranking score⁹, and weighted composite outcome¹⁰).

The primary safety outcome (28-day all-cause mortality) is based on assessing non-inferiority and we specify the null hypothesis that the biomarker interventions are much worse compared with standard-of-care. The primary safety outcome will be analysed using mixed effect logistic regression models, using the same adjustments variables as the primary effectiveness analysis. We will derive risk difference from the fitted logistic regression model to compare the non-inferiority margin for the safety outcome. The unadjusted and adjusted estimates and the 95% confidence intervals will be compared with the non-inferiority margin to accept/reject the null hypothesis. Therefore, our primary effectiveness outcome (antibiotic duration) will not provide all the information as regards the treatment effect. Safety (28-day all-cause mortality) is paramount - only if an intervention arm is not worse than the control (standard care only) will it be acceptable.

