randomisation dates and times. In the event that stop dates are unobtainable and thus missing, we will first look to see if the participant either withdrew completely or died. If so, we will use the withdrawal/death date as the stop date to estimate the duration for a particular course of antibiotics. If they did not withdraw or die, then we would impute the duration for that particular course of antibiotics using the mean duration of all antibiotics for the participant.

The SOFA score is to be collected baseline at day 3 and day 7, however, date may not be available on these particular days hence this score would be missing. In this situation, we'll use the value from the day before. If this is not available, then we'll use the value of the day after. If neither are available, then the value for that particular day will be missing.

Additional analyses

The primary analysis looks at the total duration of antibiotic days from randomisation to day 28. However, it is also of interest to assess the duration of antibiotics during the intervention phase only i.e., when the biomarker guidance is in use, and also from randomisation to ICU discharge. Therefore, additional analyses will estimate the treatment effect for the duration of antibiotic days during the intervention phase only and also to the point of ICU discharge. Similarly, we will also estimate the same treatment effects for the daily defined dose (DDD) secondary outcome.

The impact of COVID-19 pandemic on the trial will be assessed on completion of the trial. The baseline demographics and primary outcomes for participants recruited before COVID-19 will be compared to those recruited during COVID-19. The objective is to assess if there is any change in the population considered for the trial. In addition, for participants recruited during the COVID-19 pandemic period, baseline demographics and primary outcomes will be compared for COVID positive versus COVID negative participants. We also perform a sensitivity analysis by dropping COVID positive participants to see if COVID pandemic has an impact on the trial. We will do a sensitivity analysis to account for the non-compliant sites with PCT testing during intervention and follow-up phase. The plan is to run the primary outcome analysis excluding the non-compliant sites and see if any difference between the arms.

Safety

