	Missing	xx.xx	xx.xx	xx.xx	xx.xx
Time from first research blood sample taken for the trial to first research blood sample delivered					
	N	xx.xx	xx.xx	xx.xx	xx.xx
	Mean (SD)	xx.xx	xx.xx	xx.xx	xx.xx
	Median (IQR)	xx.xx	xx.xx	xx.xx	xx.xx
	Missing	xx.xx	xx.xx	xx.xx	xx.xx

SECTION 3 - PARTICIPANT FOLLOW-UP

Table 8: Follow-up rates throughout the trial

Treatment Group	Time-point	Total to reach time point	Completed	Withdrawn completely	Deceased	Incomplete data
Standard Care	Baseline	N	n (%)	n (%)	n (%)	n (%)
	28 days	N	n (%)	n (%)	n (%)	n (%)
	90 days	N	n (%)	n (%)	n (%)	n (%)
PCT	Baseline	N	n (%)	n (%)	n (%)	n (%)
	28 days	N	n (%)	n (%)	n (%)	n (%)
	90 days	N	n (%)	n (%)	n (%)	n (%)
CRP	Baseline	N	n (%)	n (%)	n (%)	n (%)
	28 days	N	n (%)	n (%)	n (%)	n (%)
	90 days	N	n (%)	n (%)	n (%)	n (%)

Table 9: Overall summary of withdrawals by treatment arm*

Withdrawal decision	Withdrawn from intervention only but remains on follow-up			Withdrawn from intervention completely and will not be followed-up		
	Standard care	PCT	CRP	Standard care	PCT	CRP
Participant's decision						
Consultee's decision						
Clinical team decision						
Antibiotics stopped due to futility						
Determined to require long term antibiotics (>21 days) after randomisation						
Other						

* Summary of total number of withdrawal requests i.e. participants may have more than one request

Table 10: Primary cause of death summarised by treatment arm

	Standard care	PCT	CRP	TOTAL	P-value
Sepsis or sepsis related (including organ/multi-organ failure)	n (%)	n (%)	n (%)	N	
Not related to sepsis	n (%)	n (%)	n (%)	N	

Table 11: Number of participant's withdrawing completely throughout the trial

	Standard care	PCT	CRP	TOTAL	P-value
Post-randomisation to ICU discharge	n (%)	n (%)	n (%)	N	
ICU discharge to Hospital discharge	n (%)	n (%)	n (%)	N	
Hospital discharge to 28 day follow-up	n (%)	n (%)	n (%)	N	
28 day follow-up to 90 day follow-up	n (%)	n (%)	n (%)	N	
Overall	n (%)	n (%)	n (%)	N	

Table 12: Number of deaths throughout the trial

	Standard care	PCT	CRP	TOTAL	P-value
Post-randomisation to ICU discharge	n (%)	n (%)	n (%)	N	
ICU discharge to Hospital discharge	n (%)	n (%)	n (%)	N	
Hospital discharge to 28 day follow-up	n (%)	n (%)	n (%)	N	
28 day follow-up to 90 day follow-up	n (%)	n (%)	n (%)	N	
Overall	n (%)	n (%)	n (%)	N	

Table 13: Time from randomisation to death, withdrawal and follow-up summarised by treatment arm

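### A missing stop date is set to the date of complete withdrawal, so a course still running is scored as finished; the fallback rule can give no value, and neither rule is tested.

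*SAP*

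**What the plan says.** Under Outcome definitions, the SAP makes the primary effectiveness outcome the sum of all course durations between randomisation and day 28. Analysis methods applies it to everyone randomised.

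Handling missing data deals with an unobtainable stop date in two steps. The first asks whether the person left the trial altogether or died, and for those who did the rule is: "If so, we will use the withdrawal/death date as the stop date to estimate the duration for a particular course of antibiotics". For everyone else, "we would impute the duration for that particular course of antibiotics using the mean duration of all antibiotics for the participant".

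Withdrawal and follow-up distinguishes two kinds of withdrawal: "They can either withdraw from the intervention alone but remain on follow-up or they can withdraw completely from the trial". The same section keeps participants in follow-up, where possible, unless they explicitly withdraw consent. Among the withdrawal reasons to be tabulated is "required >21 days of antibiotics post randomisation". Template Table 9 carries the row "Determined to require long term antibiotics (>21 days) after randomisation" under both column groups: withdrawal from the intervention with follow-up continuing, and complete withdrawal without follow-up.

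The sensitivity analyses named in the SAP concern the antibiotic start date (amendment table), deaths (Analysis methods), COVID-positive participants and sites not compliant with PCT testing (both Additional analyses). None concerns the stop date assumed after withdrawal or the own-mean rule.

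**The concern.** Complete withdrawal ends data collection; it does not end treatment. If a course is open on that day, the trial knows only that its duration is at least the days seen so far. Entering that lower limit as the observed value turns a censored duration into a complete one in the primary outcome.

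Withdrawal may also be linked to the outcome. Table 9 leaves room for a participant who withdraws completely because long treatment is needed. The trial would then hold a record of long use and score that person as a short user.

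The own-mean rule has two gaps. It has nothing to average when the only course is the one without a stop date, although the analysis is meant to include all randomised participants. It also has no floor, so the imputed duration can be shorter than the days on which antibiotics were already recorded.

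At stake is the size of the difference in antibiotic days, and whether a reader can tell how far it depends on filled dates.

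**Working it through.** The plan attaches no figure to these rules, so there is none to reproduce.

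**Inputs from the SAP (Sample size; Trial design).** Target difference 1 day; SD 6 days; total 2760 allocated 1:1:1, so 2760 / 3 = 920 per arm; planned withdrawal 5%.

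**Inputs not in the SAP (assumed).** The share p of an arm whose stop date is filled with the withdrawal date while a course is open, and the mean days m missed after withdrawal. I take p = 2% or 5%, and m = 3, 7, 14 or 21 days.

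**One participant.** Suppose complete withdrawal on day 7 (assumed), no stop date, and a true duration of 21 to 28 days. The rule scores 7 days. Shortfall: 21 − 7 = 14 to 28 − 7 = 21 days.

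**One arm.** Shift in the arm mean = −p × m.

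| p | m = 3 | m = 7 | m = 14 | m = 21 |
|---|---|---|---|---|
| 2% | −0.06 | −0.14 | −0.28 | −0.42 |
| 5% | −0.15 | −0.35 | −0.70 | −1.05 |

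**Treatment difference (biomarker minus standard care).** Shift = −(p_bio × m_bio − p_std × m_std).

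- Equal p and equal m: shift = 0.
- p_bio = 5%, p_std = 2%, same m: −0.03 × 7 = −0.21; −0.03 × 14 = −0.42; −0.03 × 21 = −0.63 days. This flatters the biomarker arm.
- p_bio = 2%, p_std = 5%: +0.21, +0.42, +0.63 days. This works against the biomarker arm.

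**Scale.** Standard error of the difference = 6 × √(2/920) = 0.280 days. The range 0.21 to 0.63 is therefore 0.21/0.280 = 0.75 to 0.63/0.280 = 2.25 standard errors.

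**How extreme the inputs are.** A 5% share needs every planned withdrawal in that arm to be complete, with a course open and no stop date. An average of 21 days missed needs all of them to withdraw by about day 7 and stay on antibiotics to day 28. The upper end is a limit, not an expectation.

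**The other direction.** Withdrawal and follow-up counts withdrawals between discharge and day 28. A course taken home and finished before such a withdrawal, with no stop date recorded, is scored as running to the withdrawal date and is too long.

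**Own-mean rule.** With one course and no stop date, the mean is over zero known durations and is undefined. With one closed course of 3 days and an open course already observed for 7 (both assumed), the rule imputes 3 days, 4 fewer than were seen.

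**The case against.** The strongest defence is that the rule reaches few people. It needs both an unobtainable stop date and complete withdrawal, and the default is to go on following participants who leave the intervention. A Table 9 cell for complete withdrawal because of long antibiotic need shows that the case is allowed, not that it will occur. This stands: a reader might infer that participants needing more than 21 days are generally scored as short users, but by default their stop dates are still collected.

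A reader might also infer that the error always shortens duration and so supports the superiority claim. Neither part follows. A course finished before a later withdrawal is lengthened, and superiority rests on the difference between arms. If withdrawal shares and timing are the same in each arm, cutting at withdrawal removes, if anything, more days from the arm with the longer true duration. With 5% withdrawing in each arm and a true 1-day difference, that is at most about 0.05 × 1 = 0.05 days, against the intervention.

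Finally, a reader might extend the criticism to deaths, because Analysis methods says of death before discontinuation that "In such cases the outcome is undefined and is referred to as" truncated by death. The SAP does not support that extension. For someone who dies on antibiotics, the date of death is when antibiotics actually ended. The warning about bias concerns a crude comparison of survivors, whereas the fill-in rule keeps those who died in the analysis. Replacing the outcome with one that scores death as zero would change the estimand.

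What the defence leaves unanswered is that the value for an open course is a lower limit entered as an observation, that the own-mean rule can be undefined, and that nothing planned tests either.

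**Conclusion.** The point holds for two things: courses still open at complete withdrawal without a stop date, and the own-mean rule for other missing stop dates. The first understates those durations; the second can return no value or an impossibly low one.

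Bias in the treatment difference is possible but not shown. It depends on between-arm differences in filled dates or days missed, for which the SAP gives no figures, and its sign is open. Under the assumed 5% v 2% imbalance it is 21% to 63% of the target effect; under balance it vanishes. The reason to act is that a pre-specified primary analysis should not rely on balance that it neither checks nor tests.

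**What to change.** Amend Handling missing data, before arm-level withdrawals are known, as follows.

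- For complete withdrawals with a course open at withdrawal, and for all other missing stop dates, multiply impute total duration. Use arm, baseline covariates, days on antibiotics so far and withdrawal reason. Bound each value below by the days already observed and above by day 28, or by death if it is known and earlier.
- Keep the present rule as a sensitivity analysis, and state what it does when a participant's only course has no stop date.
- Add a bounding analysis for open courses, from stop at withdrawal to continued to day 28.
- Report the number of filled stop dates by arm and withdrawal reason.

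The handling of deaths need not change for this point. The cost is SAP wording, some programming and slightly wider intervals; no new data are needed.

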The ADAPT-Sepsis is a multi-centre three-arm randomised controlled trial with internal pilot. Participants are randomly allocated using a ratio 1:1:1 to CRP: PCT: Usual care. A computerised minimisation randomisation system was used, created by the Warwick Clinical Trials unit, to randomise participants. The randomisation allocation was made following consent processes and baseline assessments. Stratification factors were (i) sepsis severity (sepsis or septic shock), (ii) recruitment centre and (iii) surgery within the last 72 hours or not.

Primary and secondary outcomes

The primary outcomes are effectiveness outcome of total duration of antibiotics used to 28 days post randomisation and safety outcome of 28 days all-cause mortality. Secondary outcomes include escalation of care/re-admission; infection re-lapse/recurrence; dose of antibiotics; length and level of critical care stay, length of hospital stay, and 90-days all-cause mortality.

Sample size

A total sample size of 2760 would be able to detect both a mean of 1-day reduction in antibiotic use duration (using a mean antibiotic duration of 7 days, a pooled standard deviation of 6 days, 90% power, a significance level of 5%, with a 5% withdrawals rate) and a non-inferiority safety margin of 5.4 % (using a 1-sided significance level of 2.5%, 90% power and 5% withdrawal rate) assuming 28-day mortality is 15%.

Timing of final analysis

The end of the trial is defined when the last recruited participant completed 28-days follow-up post randomisation. Once all the data have been entered onto the database, the data will be fully validated and cleaned after which the database will be locked, and the final analyses will be undertaken.

Timing of outcome assessments

Primary and secondary outcome data will be collected daily from randomisation until hospital discharge. Data will also be collected post hospital discharge up to 28-days post randomisation. All-cause mortality

will be collected at 90 days using linked data. Any SAE's will also be reported up to 28 days post-randomisation.

Reporting of results

All primary and secondary clinical effectiveness outcomes will be reported in an earlier publication, with process of care and health economics outcomes reported in subsequent publications, when all the data are available.

In addition, the sub-study, RISC-sepsis will also be reported in a further publication (and has its own approved statistical analysis plan).

Statistical principles

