- Process of care/adherence variables:

Time from:

- Hospital admission to ICU/HDU admission
- Hospital admission to first diagnosis of suspected sepsis or suspected septic shock
- Randomisation to first research blood sample taken
- First blood sample taken to first blood sample delivered to laboratory

Analysis

Outcome definitions

The primary outcomes of the trial are (i) total duration of antibiotic treatment to 28 days following randomisation (superiority) measured in days as primary clinical effectiveness outcome, and (ii) 28-day all-cause mortality (non-inferiority) following randomisation as primary safety outcome. For the clinical effectiveness outcome, the use of antibiotics data will be recorded to the point where the participant stopped antibiotics. The use of antibiotics will also be recorded if participants either restarts antibiotics in hospital or discharged from hospital and the re-admitted and receives systemic antibiotics or discharged with antibiotics provided that these events are within 28 days following randomisation. The duration of antibiotics use will be calculated for each participant as the sum of the duration of each course of antibiotics administered from randomisation to day 28. For the safety outcome, all-cause mortality status on day 28 following randomisation will be recorded.

The Secondary effectiveness and safety outcome measures to 28 days following randomisation are

- Antibiotic duration and dose for the initial sepsis episode (duration in days from randomisation and dose measured as Defined Daily Dose)
- Antibiotic dose (measured as Defined Daily Dose)
- Unscheduled care escalation/re-admission
- Infection relapse/recurrence requiring further antibiotic treatment
- Super-infection defined as new infection at a different anatomical site
- Suspected antibiotic adverse reactions
- Time to 'fit' for hospital discharge

The 90-days all-cause mortality will also be analysed as secondary outcome using linked data, for example, from NHS Digital and the Intensive Care National Audit and Research Centre.

Analysis methods

Participants' baseline characteristics and outcomes will be summarised mean and standard deviation if data are continuous or frequency and percentage if data are categorical. The median and interquartile range will be presented if data are non-normal.

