Secondary outcomes will be assessed using an ITT approach. Continuous secondary outcomes will be analysed in the same way to the primary outcome and the categorical outcomes will be assessed using mixed effects logistic regression models. Time-to-event outcomes will be analysed using Cox

proportional hazards models. For all analyses, the adjusted effect estimates will be presented along with their associated 95% confidence interval (CI). In addition, the primary outcomes will also be analysed using Bayesian method as secondary analysis considering both non-informative and informative priors.

Exploratory sub-group analyses for primary effectiveness outcome will be reported using 99% confidence intervals. Linear mixed effect regression will be used with interaction terms (treatment group by sub-group) to estimate sub-group effects. The following sub-groups selected from a recent report about the management of infection causing sepsis in the NHS will be explored:

- Community-acquired pneumonia (CAP)
- Hospital-acquired pneumonia (HAP)
- Urinary tract infection (UTI)
- Intra-abdominal infection
- Infection with positive blood culture

In addition, community acquired, hospital acquired infections and SARS-COV-2 will be analysed as subgroup. Moreover, we will do the following subgroups analysis

- Sepsis vs Septic Shock
- Ward vs ICU where the intervention was stopped
- Surgery vs non-surgery on previous 72 hours

An exploratory analysis will be done to investigate weekend effect on the primary effectiveness outcome, the total duration of antibiotic treatment to 28 days from randomisation. Monitoring of the protocol processes and compliance measures is important in this trial (as detailed in section 4). These measures will be monitored and reported to the DMC throughout the trial. A final summary of the protocol processes and compliance will be presented at the end of the trial.

Handling missing data

Every effort will be made to minimise missing data both in baseline and outcome in the trial. Missing data will be assessed carefully. For the primary outcome (duration of antibiotics), start and stop dates for each course of antibiotics are required in order to compute the total duration for each participant. There will be no missing for start dates as the start dates and times will be the

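### For participants who neither withdrew nor died, the rule for a missing antibiotic stop date has no value when no other duration is known, and no floor at the days already recorded

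*SAP*

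**What the plan says.** The Outcome definitions section defines the primary effectiveness outcome as "the sum of the duration of each course of antibiotics administered from randomisation to day 28". Use after discharge counts too, including for participants "discharged with antibiotics provided that these events are within 28 days following randomisation".

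Handling missing data says that "start and stop dates for each course of antibiotics are required in order to compute the total duration for each participant". If a stop date cannot be obtained, there are two branches. For participants who withdrew completely or died, "we will use the withdrawal/death date as the stop date to estimate the duration for a particular course of antibiotics"; that branch is not in question here. For everyone else, the stated step is to "impute the duration for that particular course of antibiotics using the mean duration of all antibiotics for the participant". Nothing follows for a participant with no known duration, and no lower limit is placed on the imputed value.

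Two other statements bear on this. Timing of outcome assessments says "Primary and secondary outcome data will be collected daily from randomisation until hospital discharge", with further collection after discharge to day 28. Analysis methods says "ITT analysis will consist of all randomised patients". The March 2023 amendment concerning antibiotic dates deals with start dates only.

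**The concern.** An imputation rule for a primary outcome should give a value, or an explicit instruction to leave it missing, for everyone it covers. It should also never override what was observed. This rule can fail on both counts.

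Where no duration is known, the analyst has to devise the handling after the data are in. The next paragraph of the same section shows how such a rule can be closed: for a missing SOFA score it names a first substitute, then a second, then says the value stays missing. The primary outcome has no such last step.

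Where other durations are known, the rule uses only those and ignores the open course itself. If the daily record already shows that course running longer than the participant's mean, the imputed total is known to be too short. The error goes straight into the primary outcome. The SAP's sensitivity analyses (deaths, COVID-positive participants, sites not compliant with PCT testing) do not vary the stop-date rule, so a distortion would not show.

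**Working it through.** The SAP gives no rate of missing stop dates and no figure for the effect of this rule, so there is nothing of its own to reproduce. The check applies the rule as written.

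**Inputs from the SAP.** The own-mean rule and who it covers (Handling missing data); the outcome as a sum of course durations to day 28 (Outcome definitions); daily collection to discharge (Timing of outcome assessments); all randomised patients analysed (Analysis methods); a target difference of 1 day, mean 7 days and SD 6 days (Sample size).

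**1. No known duration.** With k antibiotics of known duration, the imputed value is (sum of the k durations)/k. If the only antibiotic is the one with the missing stop date, k = 0 and the value is 0/0, which is undefined. Table 21 has a row for missing values, but no text assigns this case to it, and the analysis set includes the participant.

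**2. Value below the recorded days (constructed examples).**
- Drug A runs from day 0 to day 3, so 3 days. Drug B starts on day 3, is still given at discharge on day 10, and its stop date is not obtained. Recorded minimum for B: 10 − 3 = 7 days. Rule: mean of {3} = 3 days, so B ends on day 6. Shortfall: at least 7 − 3 = 4 days. Total: 3 + 3 = 6 days against at least 3 + 7 = 10.
- Completed courses of 2 and 3 days, and a third recorded for 10 days with no stop date. Rule: (2 + 3)/2 = 2.5 days. Shortfall: at least 10 − 2.5 = 7.5 days.

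**3. How readily this happens (simulation on assumed data).** Course lengths were drawn as independent gamma variables with mean 7 and SD 6, capped at 28 days. The mean and SD are borrowed from the sample-size section, where they describe total duration and not single courses. The table gives the share of cases in which the imputed length fell below the recorded days.

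| Courses per participant | Half of open course recorded | 80% of open course recorded |
|---|---|---|
| 2 | 30.2% | 43.3% |
| 3 | 22.4% | 37.5% |
| 4 | 19.2% | 34.9% |

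So a conflict with recorded days is not a rare corner case under these assumptions, though it is a minority of cases.

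**4. Scale against the 1-day target (all inputs assumed).** Shift in an arm mean = proportion affected × days lost per affected participant.
- 2% × 2 days = 0.04 day; 10% × 7 days = 0.70 day.

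Bias in the comparison = difference in proportions × days lost.
- (0.10 − 0.05) × 4 = 0.2 day; (0.20 − 0.10) × 4 = 0.4 day.
- Equal proportions and equal losses in both arms: 0.

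**The case against.** Several points on the other side have force.

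- **Day 28.** A reader might infer that the imputed course can run past day 28 and inflate the outcome. The outcome definition already restricts the sum to antibiotics given from randomisation to day 28, so later days fall outside it whatever length is imputed. That reading is not supported.
- **Post-discharge gaps.** It is tempting to say that missing stop dates must cluster after discharge because daily collection ends there. But the SAP also provides for collection after discharge up to day 28, and the rule applies only when a date cannot be obtained. The documents do not say where or how often that happens.
- **Course and antibiotic.** The rule fills a course from the mean over all the participant's antibiotics. If one course can contain several antibiotics, a one-course patient may still have durations to average. The undefined case is certain only where no other antibiotic has a known duration, and the point is limited to that.
- **The daily record.** The SAP says outcome data are collected daily. It does not show that each drug is logged each day, and Table 14, the daily-data table, lists patient status only. The floor is therefore available only where such records exist. Table 18 does show that discharge on systemic antibiotics is recorded.
- **Direction.** An own-mean can overshoot as well as undershoot. The examples were chosen to show undershoot.

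These points limit the reach and size of the concern. They do not supply the missing fallback or the missing floor.

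**Conclusion.** The point holds in a limited form. For participants who neither withdrew nor died, the stated rule is undefined when no other antibiotic has a known duration, and it can return a duration shorter than the one already recorded. Both follow from the text and bear on the primary effectiveness outcome. That the rule can undershoot recorded days is a possibility, not a certainty, and it rests on daily antibiotic records being available for the open course.

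The size is unknown. The number of missing stop dates, the days lost per case and any imbalance between arms are not in the SAP. The 0.2 and 0.4 day figures only show what assumed rates would do against a 1-day target. A reader might infer that the treatment difference will be biased. That would need the error to differ between arms, and nothing in the SAP shows that it does. The rule should be changed because it is incomplete and can contradict observed data, and because the repair is cheap.

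**What to change.** Replace the branch for participants who neither withdrew nor died with wording such as:

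> The imputed stop date will be no earlier than the last day the antibiotic is recorded as given (including discharge on antibiotics) and, as in the outcome definition, no later than day 28. Within these bounds it will be multiply imputed from participants with known stop dates, including when the participant has no other known duration.

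Name the variables in the imputation model. Treatment arm, infection site and discharge on antibiotics already appear in the template tables.

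Add two bounding sensitivity analyses for the primary effectiveness outcome: every missing stop date in this branch set to the last known day, and every one set to day 28. Report the number of imputed stop dates by arm, so that readers can judge whether the rule matters.

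The cost is a short SAP amendment, a little more programming, and multiple imputation in place of a single filled value. No new data collection is needed where the daily record and discharge status are held.
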